4.7. Efficacy Analyses

Efficacy analysis will be conducted using the Safety Analysis Set.

4.7.1. Primary Efficacy Variables

4.7.1.1. Treatment Responders

The number and proportion of patients who are considered treatment responders will be summarized descriptively separately for each phase. Treatment responders are defined as those free of spasms and have resolution of hypsarrhythmia at the end of the 2-week treatment period, as determined by video-EEG. Resolution of hypsarrhythmia requires reduction of the EEG background below 300 μV and elimination of any electrodecrements or epochs of discontinuity. Persistence of some background slowing and interictal epileptiform discharges may be seen and still be consistent with resolution of hypsarrythmia.

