9.1.2.8 Visit 11 (Day 295 [±7 Days])

This visit will occur 294 (\pm 7) days after Visit 2. The following will be collected/assessed:

- Concomitant medication review (Section 9.2.5).
- Physical examination (Section 9.2.6).
- Vital signs (Section 9.2.7).
- ECG (Section 9.2.8).
- Video-EEG (Section 9.2.9).
- Clinical laboratory samples (blood and urine [if possible]; Section 9.2.10) for:
 - Serum biochemistry.
 - Hematology.
 - Urinalysis.
- CGIC (Section 9.2.12.1).
- PGIC (Section 9.2.12.2).
- Caregiver diary review (Section 9.2.13) for:
 - Spasm/seizure information.
 - IMP usage.
 - Changes in concomitant AEDs.
 - Usage of rescue medication.
 - AEs.

• AEs (Section 12).

All IMP will be collected and compliance reviewed. Patients will then receive sufficient IMP for 12 weeks of dosing.

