1.2.2.2. Secondary Objectives

- **Key:** To assess the number and proportion of patients who are free of clinical spasms, as observed on video-electroencephalography (video-EEG) at the end of the treatment period.
- **Key:** To assess the number and proportion of patients who have resolution of hypsarrhythmia, as observed on video-EEG at the end of the treatment period.
- To assess changes in spasms and seizure subtypes by caregiver observation during the treatment period.
- To determine time to cessation of spasms during the treatment period, as determined by caregiver diaries.
- To explore the effect of GWP42003-P on quality of life.
- To assess the number and proportion of patients who are free of spasms and have resolution of hypsarrhythmia, after 3, 6, 9 and 12 months of treatment.
- To assess the number and proportion of responders who relapse and the time to relapse.
- To explore the effect of GWP42003-P on growth, adaptive behavior and development.
- To determine the population POPPK of CBD and its metabolites (6-OH-CBD, 7-COOH-CBD and 7-OH-CBD)

GW Research Ltd Study Code: GWEP15100 EudraCT Number: 2015-004904-50 25SEP2019

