2.6. Secondary Endpoints

2.6.1. *Pilot Phase*

For the pilot phase, the following secondary endpoints will be analyzed descriptively only:

- The number and proportion of patients who are free of clinical spasms, as observed on video-EEG at the end of the treatment period.
- The number and proportion of patients who have resolution of hypsarrhythmia, as observed on video-EEG at the end of the treatment period.
- Changes in spasms and seizure subtypes by caregiver observation during the treatment period.
- Time to cessation of spasms during the treatment period, as determined by caregiver diaries.
- CGIC.
- PGIC.

2.6.2. *OLE Phase*

For the OLE phase, the following secondary endpoints will be analyzed descriptively only:

- The number and proportion of patients who are free of clinical spasms, as observed on video-EEG at the end of the treatment period.
- The number and proportion of patients who have resolution of hypsarrhythmia as, observed on video-EEG at the end of the treatment period.
- Changes in spasms and seizure subtypes by caregiver observation during the treatment period.
- Time to cessation of spasms during the treatment period, as determined by caregiver diaries.
- The number and proportion of patients who are free of spasms and have resolution of hypsarrhythmia, as determined by video-EEG after 3, 6, 9 and 12 months of treatment.

GW Research Ltd Study Code: GWEP15100 EudraCT Number: 2015-004904-50

25SEP2019

- The number and proportion of responders with relapse of spasms, and the time to relapse, as determined by caregiver diaries.
- Changes from baseline in length (height), body weight, and head circumference.
- CGIC.
- PGIC.
- Change from baseline in Vineland-II score.

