4.7.2. Key Secondary Efficacy Variables

4.7.2.1. Clinical Spasms

The number and proportion of patients who are free of spasms, as observed on video-EEG at the end of the treatment period, as observed on video-EEG at the end of the treatment period, and after 3, 6, 9, and 12 months of treatment will be summarized separately for each phase.

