4.7.2.2. Hypsarrhythmia

The number and proportion of patients who have resolution of hypsarrhythmia, as observed on video-EEG at the end of the treatment period, and after 3, 6, and 12 months of treatment will be summarized separately for each phase.

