5. CHANGES TO PLANNED ANALYSES

Since this trial only included patients from the open-label pilot study, the details and analyses of the pivotal phase of the study mentioned in the protocol were omitted from this SAP.

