6. CLINICAL STUDY REPORT APPENDICES

6.1. Planned Tables

- Table 1.1 Summary of Patient Disposition All Screened Subjects
- Table 1.2 Summary of Protocol Deviations All Enrolled Subjects
- Table 2.1 Summary of Demographic Data Safety
- Table 3.1 Summary of Previous Significant Non-Epilepsy Medical or Surgical History Now Resolved Safety
- Table 3.2 Summary of Significant Non-Epilepsy Medical or Surgical History Current Conditions Safety
- Table 4.1 Summary of Prior Antiepileptic Medications and Therapies Safety
- Table 4.2 Summary of Concomitant Antiepileptic Therapies Safety
- Table 4.3 Summary of Concomitant Antiepileptic Medications Safety
- Table 4.4 Summary of Concomitant Rescue Medications Safety
- Table 4.5 Summary of Other Concomitant Medications Safety
- Table 7.1 Summary of Exposure and Compliance to Study Treatment Pilot Phase Safety
- Table 7.2 Summary of Exposure and Compliance to Study Treatment OLE Phase Safety
- Table 8.1.1 Proportion of Treatment Responders Pilot Phase Safety
- Table 8.1.2 Proportion of Treatment Responders OLE Phase Safety
- Table 9.1.1 Proportion of Spasms and Seizure Subtypes by Caregiver Observation Pilot Phase Safety
- Table 9.1.2 Proportion of Spasms and Seizure Subtypes by Caregiver Observation OLE Phase Safety
- Table 9.2.1 Summary of CGIC Scores Pilot and OLE Phase Safety
- Table 9.2.2 Summary of PGIC Scores Pilot and OLE Phase Safety
- Table 9.3 Summary of Vineland Adaptive Behavior Scales Change from Baseline by Visit OLE Phase Safety
- Table 11.1.1 Overview of Adverse Events Pilot Phase Safety
- Table 11.1.2 Overview of Adverse Events OLE Phase Safety
- Table 11.2.1 Treatment-Emergent Adverse Events by System Organ Class and Preferred Term Pilot Phase Safety
- Table 11.2.2 Treatment-Emergent Adverse Events by System Organ Class and Preferred Term OLE Phase Safety
- Table 11.3.1 Treatment Related Treatment-Emergent Adverse Events by System Organ Class and Preferred Term Pilot Phase Safety
- Table 11.3.2 Treatment Related Treatment-Emergent Adverse Events by System Organ Class and Preferred Term OLE Phase Safety
- Table 11.4.1 Treatment-Emergent Adverse Events by System Organ Class and Preferred Term and Severity Pilot Phase Safety
- Table 11.4.2 Treatment-Emergent Adverse Events by System Organ Class and Preferred Term and Severity OLE Phase Safety
- Table 11.5.1 Treatment-Emergent Adverse Events by System Organ Class and Preferred Term and Sex Pilot Phase Safety

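### SAP 4.7.1.1 fixes the treatment-responder definition at 2 weeks but also applies it to the open-label extension, and 4.7.2.2 omits month 9 for hypsarrhythmia

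*SAP*

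**What the plan says.** The SAP lists the OLE composite twice. The OLE secondary objectives (1.2.2.2) ask how many patients are spasm-free and "have resolution of hypsarrhythmia, after 3, 6, 9 and 12 months of treatment". The OLE endpoint list (2.6.2) repeats this "as determined by video-EEG after 3, 6, 9 and 12 months of treatment" and says the OLE secondary endpoints are analyzed descriptively. Protocol 4.1.2.3 and 13.6.3.3 give the same composite at the same four times.

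The methods then read differently:

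- 4.7.1.1 defines the composite once, for use in each phase: "Treatment responders are defined as those free of spasms and have resolution of hypsarrhythmia at the end of the 2-week treatment period".
- 4.7.2.1 takes the spasm component at end of treatment "and after 3, 6, 9, and 12 months of treatment will be summarized separately for each phase".
- 4.7.2.2 takes the hypsarrhythmia component at end of treatment "and after 3, 6, and 12 months of treatment will be summarized separately for each phase".

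Section 6.1 plans "Table 8.1.2 Proportion of Treatment Responders OLE Phase Safety", with Table 8.1.1 as its pilot counterpart. Section 5 declares one change, that "the details and analyses of the pivotal phase of the study mentioned in the protocol were omitted from this SAP".

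**The concern.** A table programmer works from section 4.7 and the table list. The responder rule found there suits the pilot phase, whose treatment period is 2 weeks. It was carried into the OLE without a new time point. Applied as written, it would place a pilot-phase outcome in the OLE responder table, and the four OLE time points would not appear there.

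The missing month 9 creates a second mismatch. A composite at month 9 needs both components, yet the methods would summarize spasms at month 9 without hypsarrhythmia beside them. At stake is whether the durability of response in the extension is reported as the SAP's own endpoint list promises.

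**Working it through.** The plan gives no figure to reproduce, so the check sets the sections side by side and compares them with the visit schedule.

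**Time points in the SAP**

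| SAP section | Outcome | OLE time points |
|---|---|---|
| 1.2.2.2 (objective) | Composite | 3, 6, 9, 12 months |
| 2.6.2 (endpoint) | Composite | 3, 6, 9, 12 months |
| 4.7.1.1 (method) | Composite | End of the 2-week period only |
| 4.7.2.1 (method) | Spasms | End of treatment; 3, 6, 9, 12 months |
| 4.7.2.2 (method) | Hypsarrhythmia | End of treatment; 3, 6, 12 months |
| 6.1, Table 8.1.2 | Responders, OLE | None stated |

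No other planned OLE table covers a video-EEG outcome. Table 9.1.2 reports caregiver observation, Tables 9.2.1 and 9.2.2 the global impressions, and Table 9.3 the Vineland-II.

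**Literal reading of 4.7.1.1**

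The end of the 2-week period is Visit 4, Day 15. After Visit 7 (Day 43), the protocol's Appendix 1 schedules OLE video-EEGs at Visits 9, 10, 11 and 12 (Days 127, 211, 295 and 379). The distances from Day 15 are:

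- Visit 9: 127 − 15 = 112 days
- Visit 10: 211 − 15 = 196 days
- Visit 11: 295 − 15 = 280 days
- Visit 12: 379 − 15 = 364 days

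Table 8.1.2 would hold 1 time point instead of the 4 listed, and that one belongs to the pilot phase.

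**Month 9 for hypsarrhythmia**

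Section 4.7.2.2 keeps 3 of the 4 month points. Protocol 9.1.2.8 schedules a video-EEG at Visit 11 (Day 295 ±7), so the omission does not reflect a missing assessment. The protocol's hypsarrhythmia-only OLE endpoint (13.6.3.3) is at end of treatment, so no protocol endpoint is lost. The effect is confined to the two components being reported at different times.

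**Month labels (clarification only)**

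Months from first dose = (visit day − 1) / 30.4375:

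- Visit 9: 126 / 30.4375 = 4.1
- Visit 10: 210 / 30.4375 = 6.9
- Visit 11: 294 / 30.4375 = 9.7
- Visit 12: 378 / 30.4375 = 12.4

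Counted from Day 15 instead, the values are 112, 196, 280 and 364 days divided by 30.4375, or 3.7, 6.4, 9.2 and 12.0 months. The two origins differ by 14 days, about 0.46 month. On either clock the labels are nominal, but four EEG visits match four labels in order.

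**Size**

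SAP 4.1 gives 9 pilot patients, so at most 9 enter the OLE table. One patient classified differently moves a proportion by 1/9, about 11 percentage points, or more if fewer patients continue.

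**The case against.** The best defence is that the intended analysis can be recovered from the SAP. Section 2.6.2 already gives the composite's components, instrument, time points and descriptive method, and 4.7.1.1 supplies the criteria for resolution. Day 15 belongs to the pilot phase and has its own Table 8.1.1. As the only OLE table for a video-EEG outcome, Table 8.1.2 is the natural home for the month rows. The missing month 9 looks like a typing slip: 4.7.2.1, directly above, repeats a clause, so both sentences seem poorly proofread.

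Most of this stands, and it rules out three stronger readings that a reader might infer:

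- *The SAP leaves the OLE composite unspecified.* It does not. Section 2.6.2 specifies it, and the fault is that 4.7.1.1 was not adapted to match.
- *The programmer may choose which visit counts as 3 or 6 months.* Neither document states the time origin or the visit for each month. However, SAP 4.2.10 displays by-visit data by nominal visit, and after Visit 7 only Visits 9, 10, 11 and 12 have a scheduled EEG. No competing mapping is evident. The ±7-day windows are scheduling tolerances, and the documents do not claim that the labels are exact calendar months.
- *These are undeclared changes to a protocol endpoint.* Section 2.6.2 keeps the protocol composite unchanged, and nothing in section 5 suggests a deliberate change. They read as drafting slips.

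What the defence does not remove is that two stated rules in the methods section, followed as written, give a wrong or incomplete OLE result. A reader has to override 4.7.1.1 with 2.6.2 to get the right table.

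**Conclusion.** The point holds as an internal inconsistency in the SAP. The 2-week responder definition in 4.7.1.1 conflicts with the OLE composite in 1.2.2.2 and 2.6.2, and 4.7.2.2 omits a month that the neighbouring section and the composite both need.

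The impact is minor. The endpoint is secondary and descriptive, covers at most 9 open-label patients, and involves no hypothesis test (SAP 4.2.1), so no error rate is affected. It is still worth correcting, because the fix is cheap and Table 8.1.2 is the only planned OLE summary of a video-EEG outcome.

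The conclusion rests on one inference, that 4.7.1.1 feeds Table 8.1.2. This follows from the table's title, the instruction to summarize by phase, and the absence of any other responder definition. The day counts use nominal visit days, with Day 15 as the end of the pilot phase and a month of 30.4375 days.

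**What to change.** - In SAP 4.7.1.1, limit the 2-week definition to the pilot phase.
- In the same section, define the OLE responder as a patient with no spasms and with hypsarrhythmia resolved on the same visit's video-EEG. Tabulate this in Table 8.1.2 at Visits 9, 10, 11 and 12, labelled 3, 6, 9 and 12 months.
- In 4.7.2.2, restore month 9 (Visit 11).
- As a minor clarification, add a note that the month labels are nominal and that these visits fall at about 4.1, 6.9, 9.7 and 12.4 months from first dose.

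The cost is a few sentences of SAP text and a few extra rows in Table 8.1.2. No new data are needed, and visits and treatment do not change. If the SAP can no longer be revised, protocol 13.3 provides for recording deviations from it in the clinical study report.

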4.7.2. Key Secondary Efficacy Variables

4.7.2.1. Clinical Spasms

The number and proportion of patients who are free of spasms, as observed on video-EEG at the end of the treatment period, as observed on video-EEG at the end of the treatment period, and after 3, 6, 9, and 12 months of treatment will be summarized separately for each phase.

4.7.2.2. Hypsarrhythmia

The number and proportion of patients who have resolution of hypsarrhythmia, as observed on video-EEG at the end of the treatment period, and after 3, 6, and 12 months of treatment will be summarized separately for each phase.

4.7.3. Secondary Efficacy Variables

4.7.3.1. Changes in Spasms and Seizure Subtypes

Caregivers will be instructed to record whether the patient had any episodes of spasms and/or other subtypes of epileptic seizure on a daily basis. The number and percentage of subjects who experienced spasms and other seizure subtypes (ie-Tonic, Clonic, Tonic-Clonic, Atonic, Myoclonic, Focal, Absence) during the treatment period will be summarized for each phase by visit.

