13.6.3.2 Pivotal Phase

For the pivotal phase, the number and proportion of patients who are free of clinical spasms, and the proportion of patients with resolution of hypsarrhythmia at the end of the initial 2-week treatment phase, will be analyzed by treatment group using a chi-square test. However, if the number of patients in either of the treatment groups is less than 5 then a Fisher's exact test will be performed instead.

Changes in spasms and seizure subtypes during the initial 2-week treatment phase will be analyzed descriptively only.

The time to cessation of spasms during the initial 2-week treatment phase will be calculated as the number of days from first dose of IMP to the first day in which no spasms were recorded in the patient diary. Patients who do not have cessation of spasms by Visit 4 will be censored on the day of Visit 4. The time to cessation of spasms will be analyzed descriptively as well as with a log-rank test.

The CGIC and PGIC will be analyzed by treatment group using ordinal logistic regression, including treatment group as a factor and sex as a covariate in the model.

Safety and tolerability as determined by AEs, clinical laboratory tests, 12-lead electrocardiogram (ECG), physical examinations and vital signs.

Measurement where possible of plasma concentrations of CBD and its major metabolites (7-OH-CBD, 6-OH-CBD, and 7-COOH-CBD) will be investigated using a sparse sampling approach, with the aim to define a POPPK model.

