1.2.1.2. Secondary Objectives

- **Key:** To assess the number and proportion of patients who are free of clinical spasms, as observed on video-electroencephalography (video-EEG) at the end of the treatment period.
- **Key:** To assess the number and proportion of patients who have resolution of hypsarrhythmia, as observed on video-EEG at the end of the treatment period.
- To assess changes in spasms and seizure subtypes by caregiver observation during the treatment period.
- To determine time to cessation of spasms during the treatment period, as determined by caregiver diaries.
- To explore the effect of GWP42003-P on quality of life.

1.2.2. *OLE Phase*

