4.2.9. Baseline Definition

Unless otherwise noted, baseline (for both the pilot and OLE phases) is defined as the data most recently collected prior to the first IMP dosing start date/time in the pilot phase. If the timing of some data collection is not recorded, it will be assumed that the assessment at the first dosing date is performed as planned, i.e. prior to dosing in the pilot phase.

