4.2.10. Visit Windows

Any clinical domains that are displayed by visit will be shown by nominal study visit.

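### The SAP reduces the daily spasm diary to an any-event percentage by visit with no day window or change measure, and gives no method or table for time to cessation, relapse or time to relapse

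*SAP*

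**What the plan says.** Protocol 9.2.13.1 has the caregiver record, for each day, whether spasms or other seizure subtypes occurred. No counts are required. SAP 2.6.1 and 2.6.2 list changes in spasms and seizure subtypes as a secondary endpoint in both the pilot and the open-label extension (OLE).

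The only analysis text for the diary is SAP 4.7.3.1: "The number and percentage of subjects who experienced spasms and other seizure subtypes", per phase and by visit. SAP 4.2.10 adds: "Any clinical domains that are displayed by visit will be shown by nominal study visit". Baseline, under SAP 4.2.9, "is defined as the data most recently collected prior to the first IMP dosing start date/time in the pilot phase".

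The SAP also lists these diary endpoints:
- Pilot and OLE: "To determine time to cessation of spasms during the treatment period, as determined by caregiver diaries".
- OLE objective: "To assess the number and proportion of responders who relapse and the time to relapse".
- OLE endpoint: "The number and proportion of responders with relapse of spasms, and the time to relapse, as determined by caregiver diaries".

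SAP 4.7.3 covers only the diary percentages, the two global impression scales and Vineland-II. In SAP 6.1 the only diary efficacy tables are 9.1.1 and 9.1.2, both proportions. SAP 1.1 undertakes to set out differences from the protocol. Section 5 declares one: "the details and analyses of the pivotal phase of the study mentioned in the protocol were omitted from this SAP".

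**The concern.** There are two gaps.

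**The diary summary.** A daily yes/no record is collapsed to whether a subject had any event at a visit. A nominal visit label assigns no diary days to that visit. The baseline rule does not say whether a diary baseline is the last day before dosing or all of screening. No change statistic follows, although change is the endpoint. Protocol 6.1.4 requires spasms on the screening video-EEG, so an any-spasm measure starts at or near 100%. It then moves only when a patient has no spasm day at all in the window.

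**Listed endpoints without a method.** Someone who follows the SAP exactly produces no result for time to cessation, relapse or time to relapse, and nothing in section 5 says they were dropped. If they are reported, the rules will be chosen with open-label data already in view.

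**Working it through.** The documents give no figure for these endpoints, so there is none to reproduce.

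**Step 1: text check.**
- *Cessation.* The only rule is in protocol 13.6.3.2 (pivotal phase): days from first dose to the "first day in which no spasms were recorded in the patient diary", censored at Visit 4. Protocol 4.1.2.1 lists the endpoint for all phases, so the rule can be carried to the pilot. Visit 4 (Day 15) censoring cannot serve an OLE that runs to Day 379. Protocol 13.6.3.1 and 13.6.3.3 give no rule.
- *Relapse.* The population (responders, SAP 4.7.1.1), the event (spasms) and the source (diary) are given. Time origin, censoring and any persistence requirement are not.
- *Blank days.* SAP 4.2.8 makes no substitutions for missing data but does not say how a blank diary day counts. Read literally, the protocol rule could treat a blank day as spasm-free.

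**Step 2: visit gaps.** Visits 2 to 12 fall on Days 1, 4, 15, 19, 29, 43, 71, 127, 211, 295 and 379. The gaps are 3 and 11 days (pilot), then 4, 10, 14, 28, 56, 84, 84 and 84 days (OLE).

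**Step 3: what an any-event summary shows.** Let p be the share of days with spasms and r the day-to-day (lag-1) correlation. Then

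P(any spasm day in k days) = 1 − (1 − p)·(1 − p(1 − r))^(k−1).

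All values of p are assumed, because the documents give none. I use r = 0 (independent days) and r = 0.5 (clustered days).

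| Case | r = 0 | r = 0.5 |
|---|---|---|
| p = 0.90, k = 11 | ≈ 100% | ≈ 100% |
| p = 0.20, k = 11 | 1 − 0.8^11 = 91.4% | 1 − 0.8 × 0.9^10 = 72.1% |
| p = 0.05, k = 4 | 1 − 0.95^4 = 18.5% | 1 − 0.95 × 0.975^3 = 11.9% |
| p = 0.05, k = 84 | 1 − 0.95^84 = 98.7% | 1 − 0.95 × 0.975^83 = 88.4% |

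*Partial improvement.* A fall from 90% to 20% of days leaves an expected 9 × 0.914 = 8.2 or 9 × 0.721 = 6.5 of 9 patients still positive over the 11 days to Visit 4. As a percentage of diary days, the same change is −70 points.

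*Window effect.* If by visit means since the previous visit, an unchanged 5% rate shows as 12–19% over a 4-day gap and 88–99% over an 84-day gap. For frequent spasms the effect is small: at p = 0.90 even a 3-day window gives 97–99.9%.

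**Step 4: sensitivity to event definitions (same assumptions).**
- *Cessation.* With spasms on 90% of days and no drug effect, one spasm-free day within 14 occurs in 1 − 0.9^14 = 77% of patients (r = 0) or 1 − 0.9 × 0.95^13 = 54% (r = 0.5). Only 1 − 0.9 = 10% are spasm-free on the last day.
- *Relapse.* Over Days 15 to 379 (364 days) at 1% of days, a single-day rule is met by 1 − 0.99^364 = 97% (r = 0) or 1 − 0.99 × 0.995^363 = 84% (r = 0.5). A two-consecutive-day rule, from a two-state Markov chain, gives 3.5% or 60%.

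**The case against.** **Subject-level data are kept.** Listing 8.1 in SAP 6.2 covers clinical spasms and seizures, and SAP 4.2.8 sends all CRF data to listings. A reader might infer that the information will be lost; the documents do not support that. With 9 patients the listing is a real mitigation. It still supplies no event rule, time origin or censoring, and its layout is not specified.

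**The SAP contradicts no protocol statistic.** The protocol also leaves changes in spasms to description, even in the pivotal phase, so percentage of diary days is a better summary rather than a required one. Because the diary is reviewed at each visit, since the last review is a natural reading of by visit. Both points stand. The window still needs one sentence, and the SAP's measure remains weak for a change endpoint.

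**Relapse is partly specified.** A reader might infer that relapse is undefined altogether. It is not: population, event and source are stated, and a diary spasm after response is the natural reading. The gap is origin, censoring and persistence.

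**The illustrations rest on assumed rates.** That is correct. A reader might also infer that percentage of diary days would be precise in 9 patients. A standard error of about 5 to 10 points for the −70 change holds only with no between-patient variation. With an assumed between-patient SD of 30 points, 30/√9 = 10, and √(10² + 5.2²) to √(10² + 9.8²) gives about 11 to 14 points. No precision claim is made here.

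**Prespecification cannot be recovered.** The phases are open-label, and the SAP already reports 9 patients and writes of enrolment in the past tense. The gain is complete and transparent reporting.

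**Conclusion.** The point holds at moderate weight. The omission of a method and table for time to cessation, relapse and time to relapse is a matter of text and needs no assumption. Section 5 leaves it undeclared despite the undertaking in SAP 1.1. The weakness of the any-event summary follows from the inclusion criterion and the 3-to-84-day gaps. Its size is illustrative only, since it depends on assumed daily rates and, for the window effect, on reading by visit as since the previous visit.

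Scope is limited to descriptive secondary endpoints in 9 patients. A reader might infer that the trial's efficacy conclusion is at risk. It is not: the responder endpoint is read from video-EEG and does not use the diary, no error rate is involved, and the two global impression scales still describe overall change.

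**What to change.** 1. **SAP 4.7.3.1.** State the diary days that each visit covers. Add each patient's percentage of recorded diary days with spasms, and with each subtype, for three periods: screening (all recorded pre-dose days); the pilot (Day 1 to the end of the pilot evaluable period in protocol 13.6.1, so that Days 15–18 are assigned when Visit 4 is late); and fixed OLE blocks. Show the number of recorded days and the change from screening. Do not count blank days as spasm-free.
2. **Time to cessation.** Apply the rule in protocol 13.6.3.2, censored at Visit 4 for the pilot and at the end of the OLE evaluable period for the OLE. Mark patients who had already ceased at OLE entry. Add a companion column for spasm-free to the end of the phase, with run length, because that status can rest on a single last day.
3. **Relapse.** Among video-EEG responders, use the first recorded spasm day after the response EEG, censored at the end of the OLE evaluable period. Show total spasm days since response and whether IMP was being taken, since protocol 13.6.1 counts data after discontinuation for resolution of spasms. A two-consecutive-day rule is optional and only a convention; Step 4 shows how strongly it depends on clustering.
4. **Otherwise** declare and justify the omission in section 5. Either way, label added definitions as post hoc.

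Cost: SAP wording and a few descriptive tables. This assumes that the daily entries from the paper diary are in the database, which neither document states. Screening is at most 7 days, so the diary baseline will be short, and OLE block length is a convention.
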